### **Additional suggestions for sensitivity analyses**

Other suggestions for additional sensitivity analyses may include analyses to check for potential bias in follow-up schedules for tumor assessments, e.g. by assigning the dates for censoring and events only at scheduled visit dates. The latter could be handled by replacing in [Table 14-5](#) the “Date of last adequate assessment” by the “Date of previous scheduled assessment (from baseline)”, with the following definition:

- **Date of previous scheduled assessment (from baseline)** is the date when a tumor assessment would have taken place, if the protocol assessment scheme was strictly followed from baseline, immediately before or on the date of the last adequate tumor assessment.

In addition, analyses could be repeated using the Investigators’ assessments of response rather than the calculated response. The need for these types of sensitivity analyses will depend on the individual requirements for the specific study and disease area and have to be specified in the protocol or RAP documentation.

#### **14.1.4 Data handling and programming rules**

The following section should be used as guidance for development of the protocol, data handling procedures or programming requirements (e.g. on incomplete dates).

##### **14.1.4.1 Study/project specific decisions**

For each study (or project) various issues need to be addressed and specified in the protocol or RAP documentation. Any deviations from protocol must be discussed and defined at the latest in the RAP documentation.

The proposed primary analysis and potential sensitivity analyses should be discussed and agreed with the health authorities and documented in the protocol (or at the latest in the RAP documentation before database lock).

##### **14.1.4.2 End of treatment phase completion**

Patients **may** voluntarily withdraw from the study treatment or may be taken off the study treatment at the discretion of the investigator at any time. For patients who are lost to follow-up, the investigator or designee should show "due diligence" by documenting in the source documents steps taken to contact the patient, e.g., dates of telephone calls, registered letters, etc.

The end of treatment visit and its associated assessments should occur within 14 days of the last study treatment.

Patients may discontinue study treatment for any of the following reasons:

- Adverse event(s)

- Lost to follow-up
- Physician decision
- Pregnancy
- Protocol deviation
- Subject/guardian decision
- Death
- Progressive disease per irRC (not per RECIST)
- Study terminated by the sponsor

#### **14.1.4.3 End of post-treatment follow-up (study phase completion)**

End of post-treatment follow-up visit will be completed after discontinuation of study treatment and post-treatment evaluations but prior to collecting survival follow-up.

Patients may provide study phase completion information for one of the following reasons:

- Adverse event
- Lost to follow-up
- Physician decision
- Pregnancy
- Protocol deviation
- Technical problems
- Subject/guardian decision
- Death
- New therapy for study indication
- Progressive disease
- Study terminated by the sponsor

#### **14.1.4.4 Medical validation of programmed overall lesion response**

As RECIST is very strict regarding measurement methods (i.e. any assessment with more or less sensitive method than the one used to assess the lesion at baseline is considered UNK) and not available evaluations (i.e. if any target or non-target lesion was not evaluated the whole overall lesion response is UNK unless remaining lesions qualified for PD), these UNK assessments may be re-evaluated by clinicians at Novartis or external experts. In addition, data review reports will be available to identify assessments for which the investigators' or central reader's opinion does not match the programmed calculated response based on RECIST criteria. This may be queried for clarification. However, the investigator or central reader's response assessment will never be overruled.

If Novartis elect to invalidate an overall lesion response as evaluated by the investigator or central reader upon internal or external review of the data, the calculated overall lesion response at that specific assessment is to be kept in a dataset. This must be clearly documented in the RAP documentation and agreed before database lock. This dataset should be created and stored as part of the 'raw' data.

Any discontinuation due to ‘Disease progression’ without documentation of progression by RECIST criteria should be carefully reviewed. Only patients with documented deterioration of symptoms indicative of progression of disease should have this reason for discontinuation of treatment or study evaluation.

#### **14.1.4.5 Programming rules**

The following should be used for programming of efficacy results:

##### **14.1.4.5.1 Calculation of ‘time to event’ variables**

Time to event = end date - start date + 1 (in days)

When no post-baseline tumor assessments are available, the date of randomization/start of treatment will be used as end date (duration = 1 day) when time is to be censored at last tumor assessment, i.e. time to event variables can never be negative.

##### **14.1.4.5.2 Incomplete assessment dates**

All investigation dates (e.g. X-ray, CT scan) must be completed with day, month and year.

If one or more investigation dates are incomplete but other investigation dates are available, this/these incomplete date(s) are not considered for calculation of the assessment date (and assessment date is calculated as outlined in [Section 14.1.3.2.7](#)). If all measurement dates have no day recorded, the 1st of the month is used.

If the month is not completed, for any of the investigations, the respective assessment will be considered to be at the date which is exactly between previous and following assessment. If a previous and following assessment is not available, this assessment will not be used for any calculation.

##### **14.1.4.5.3 Incomplete dates for last known date patient alive or death**

All dates must be completed with day, month and year. If the day is missing, the 15th of the month will be used for incomplete death dates or dates of last contact.

##### **14.1.4.5.4 Non-target lesion response**

If no non-target lesions are identified at baseline (and therefore not followed throughout the study), the non-target lesion response at each assessment will be considered ‘not applicable (NA)’.

##### **14.1.4.5.5 Study/project specific programming**

The standard analysis programs need to be adapted for each study/project.

##### **14.1.4.5.6 Censoring reason**

In order to summarize the various reasons for censoring, the following categories will be calculated for each time to event variable based on the treatment completion page, the study evaluation completion page and the survival page.

For survival the following censoring reasons are possible:

- Alive
- Lost to follow-up

For PFS and TTP (and therefore duration of responses) the following censoring reasons are possible:

- Ongoing without event
- Lost to follow-up
- Withdrew consent
- Adequate assessment no longer available\*
- Event documented after two or more missing tumor assessments (option
- Death due to, see [Table 14-5](#)) to reason other than underlying cancer (*only used for TTP and duration of response*)
- Initiation of new anti-cancer therapy

\*Adequate assessment is defined in [Section 14.1.3.2.7](#). This reason is applicable when adequate evaluations are missing for a specified period prior to data cut-off (or prior to any other censoring reason) corresponding to the unavailability of two or more planned tumor assessments prior to the cut-off date. The following clarifications concerning this reason should also be noted:

- This may be when there has been a definite decision to stop evaluation (e.g. reason="Sponsor decision" on study evaluation completion page), when patients are not followed for progression after treatment completion or when only UNK assessments are available just prior to data cut-off).
- The reason "Adequate assessment no longer available" also prevails in situations when another censoring reason (e.g. withdrawal of consent, loss to follow-up or alternative anti-cancer therapy) has occurred more than the specified period following the last adequate assessment.
- This reason will also be used to censor in case of no baseline assessment.

## **14.2 Appendix 2: Guidelines for immune-related Response Criteria (irRC) using one-dimensional measurements (simulating RECIST 1.1)**

### **14.2.1 Introduction**

The purpose of this document is to summarize the immune-related Response Criteria (irRC) (Wolchol et al 2009) using one-dimensional measurements (Nishino et al 2013) that will be used to assess tumor response.

The definition of target/non target lesions, the criteria for lesion measurement, number of lesions that can be assessed and method of evaluation are the same for irRC and RECIST 1.1 and are available in the RECIST 1.1 guidelines (Appendix 1).

This appendix outlines the specificities for irRC evaluation.

### **14.2.2 New lesions and non-target lesions**

In irRC a new lesion does not automatically indicate progressive disease.

New measurable lesions are added to the sum of diameters of the previously existing target lesions, and the sum of diameters is followed at each subsequent tumor assessment.

New measurable lesions are defined using the same criteria as for baseline target lesions in RECIST 1.1. New measurable lesions shall be prioritized according to size, and the largest lesions shall be selected as new measurable lesions. Up to five new measurable lesions (and a maximum of two per organ) are allowed in total and will be included in the overall tumor assessment.

Non-target lesions (baseline and new non-measurable lesions) are used primarily for determination of Complete Response (CR). A CR requires that all non-target lesions disappear (both those present at baseline and any new non-measurable lesions that have appeared during the study). If after worsening a non-target lesion becomes measurable, it should still be followed as a non-target lesion. Worsening of non-target lesions and new non-measurable lesions only indicate disease progression if there is unequivocal evidence of disease progression (Table 14-6).

### **14.2.3 Follow-up evaluation of target and non-target lesions**

To assess tumor response, the sum of diameters for all target lesions is calculated (at baseline and throughout the study). The diameters of any new measurable lesions are included in the sum of diameters at each assessment to provide the total tumor burden. At each assessment, percent change in the sum of diameters is calculated and compared to baseline or to nadir in order to evaluate the target lesion response (including new measurable lesions) (Section 14.2.4). This evaluation combined with the status of non-target lesions (baseline and new non-measurable lesions) is then used to determinate the overall lesion response (Table 14-6).

#### **14.2.4 Definitions of response categories and evaluation of overall lesion response**

In irRC, the overall response is primarily based on target lesions (baseline and new measurable lesions). The non-target lesions only contribute to define irCR, and irPD in the case of unequivocal progression, as shown below in [Table 14-6](#).

Like in RECIST 1.1, irCR and irPR must be confirmed at a new assessment after at least 4 weeks. Unlike RECIST 1.1, irPD also requires confirmation at a new assessment after at least 4 weeks.

The response categories are defined as follows:

- Immune related Complete Response (irCR): Disappearance of all non-nodal target lesions and non-target lesions in two consecutive observations not less than 4 weeks apart. In addition, any pathological lymph nodes assigned as target lesions must have a reduction in short axis to < 10 mm. (Sum of diameters may be greater than zero at the time of CR, if nodal lesions are included as target lesions).
- Immune related Partial Response (irPR): At least a 30% decrease in the sum of diameters of all target lesions including new target lesions in two consecutive observations not less than 4 weeks apart, taking as reference the baseline sum of diameters.
- Immune related Progressive Disease (irPD): At least a 20% increase in the sum of diameters of all measured target lesions including new measurable lesions. The irPD must be confirmed in a second evaluation not less than 4 weeks later, taking as reference the smallest sum of diameter of all target lesions recorded at or after baseline (nadir). In addition to the relative increase of 20%, the sum must also demonstrate an absolute increase of at least 5 mm. Worsening of non-target lesions (existing or new) only indicate PD when there is unequivocal evidence of progression, confirmed in a second evaluation not less than 4 weeks later.
- Immune related Stable Disease (irSD): Neither a sufficient shrinkage to qualify for irPR or irCR, nor an increase in lesions which would qualify for irPD.
- Unknown (UNK): Progression has not been documented and one or more target lesions or new measurable lesions observed at earlier assessment have not been/could not be assessed, or have been assessed using a method significantly different from baseline (target lesions) or assessment of first occurrence (for new measurable lesions) that prevents reasonable comparison to the prior assessments.

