#### Nodal lesions

A nodal lesion less than 10 mm in size by short axis is considered normal. Lymph nodes are not expected to disappear completely, so a “non-zero size” will always persist.

Measurements of nodal target lesions that become 5 mm or less in short axis are likely to be non-reproducible. Therefore, it is recommended to report a default value of 5 mm, instead of the actual measurement. This default value is derived from the 5 mm CT slice thickness (but should not be changed with varying CT slice thickness). Actual measurement should be given for all lesions larger than 5 mm in short axis irrespective of slice thickness/reconstruction interval.

However, once a target nodal lesion shrinks to less than 10 mm in its short axis, it will be considered normal for response purpose determination. The lymph node measurements will continue to be recorded to allow the values to be included in the sum of diameters for target lesions, which may be required subsequently for response determination.

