**Table 14-6 Overall response at each assessment**

Target and new measurable lesions (Tumor burden), * (%)	Non-target lesions (both baseline and new non-measurable)	Overall lesion response
- 100	Absent	irCR a
- 100	Stable/not evaluated	irPR a
≤-30 b	Absent/Stable/not evaluated	irPR a
>-30 b and <+20 c	Absent/Stable/not evaluated	irSD
≥+20 c	Any	irPD a
Any	Unequivocal progression	irPD a

\*the diameter of new measurable lesions is included in the calculation of the sum of diameters.

a to be confirmed after at least 4 weeks.

b from baseline

c from nadir

If the evaluation of any of the target lesions could not be made during follow-up, the overall status must be ‘unknown’ unless progression was documented.

If the evaluation of any non-target lesions is not made, and all target lesions disappeared, irCR cannot be determined and overall response must be “irPR”.

In some circumstances it may be difficult to distinguish residual disease from normal tissue. When the evaluation of complete response depends on this determination, it is recommended that the residual lesion be investigated (fine needle aspirate/biopsy) to confirm the irCR.

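### Protocol Section 14.2.4 and Table 14-6 give different irRC rules for irPD (5 mm minimum) and irCR (nodal targets), and the SAP does not say which applies

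*Protocol*

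**What the plan says.** Protocol Appendix 2 works in two steps (Section 14.2.3). The percent change in the sum of diameters is calculated "in order to evaluate the target lesion response (including new measurable lesions) (Section 14.2.4"), and that result, combined with non-target status, "is then used to determinate the overall lesion response (Table 14-6"). Both places are therefore operative.

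**irPD.** Section 14.2.4 asks for at least +20%, with the nadir as reference, and then: "In addition to the relative increase of 20%, the sum must also demonstrate an absolute increase of at least 5 mm". In Table 14-6 the irPD row is a change of +20% or more from nadir with any non-target status. The irSD row ends just below +20%. Neither the footnotes nor the notes under the table mention 5 mm.

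**irCR.** In Section 14.2.4 non-nodal targets and non-target lesions must disappear, and "any pathological lymph nodes assigned as target lesions must have a reduction in short axis to < 10 mm". It adds: "Sum of diameters may be greater than zero at the time of CR, if nodal lesions are included as target lesions". The Table 14-6 row, whose first entry is minus 100 percent, reads "100 Absent irCR" and has no nodal exception.

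**Measurement.** Section 14.2.1 carries the RECIST 1.1 measurement rules over to irRC. Under those rules (Section 14.1.2.4.1) "Lymph nodes are not expected to disappear completely", and small nodes are recorded at a default of 5 mm.

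The RECIST counterpart, Table 14-1, contains both the 5 mm condition and the nodal exception. SAP 3.4 and 4.2 refer to Appendix 14.2 and define total tumour burden, but restate neither condition.

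**The concern.** Two readers following the same appendix can assign different irRC responses to the same measurements. Responses are assigned by local investigators (Protocol 7.2.1), so sites could differ from one another, and an analysis program could differ from both.

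The exposed results are the irRC versions of PFS, DOR and BOR. An irPD sets the event date and ends the assessments that count for irRC BOR (SAP 4.2.3). Patients with a low nadir sum include those whose tumours shrank most, so an irPD defined by percentage alone falls partly on good responders. For irCR, a patient whose remaining nodes are of normal size would be tabulated as irPR.

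Progression per irRC is also a criterion in treatment discontinuation (Protocol 4.1 and 7.1.4). For that use, the point here is only that the two passages must be reconciled.

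**Working it through.** No sample size, power or error rate in the plan depends on this point, so there is no plan figure to reproduce. The check applies the two rules to the same measurements.

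**1. Where the irPD rules differ.** The text needs an increase of max(5 mm, 0.20 x nadir); the table needs 0.20 x nadir. They differ when 0.20 x nadir < 5 mm, that is, when nadir < 5/0.20 = 25 mm.

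| Nadir (mm) | Table needs | Text needs |
|---|---|---|
| 10 | +2.0 mm | +5 mm |
| 12 | +2.4 mm | +5 mm |
| 15 | +3.0 mm | +5 mm |
| 20 | +4.0 mm | +5 mm |
| 25 | +5.0 mm | +5 mm |

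**2. Worked records for irPD.**
- Baseline 14, nadir 12, now 15 mm: +3 mm, 3/12 = +25% from nadir. Table: irPD, the only row that fits. Text: irSD.
- Nadir 12, now 14.5 mm: +2.5 mm, 2.5/12 = +21%. Text: not irPD. The table's irPD row is met. If the baseline was at least 14.5/0.7 = 20.7 mm, the sum is also at least 30% below baseline, so the irPR row is met too (non-targets absent, stable or not evaluated). The table states no precedence between the two rows.
- Sole target a 15 mm node, recorded at 5 mm and then 6 mm, no other disease: 1/5 = +20% from nadir. The irPD row is met, and at (15-6)/15 = 60% below baseline so is the irPR row. Text: irCR, because the node is below 10 mm.

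**3. irCR.** A nodal target keeps a non-zero size, so -100% cannot be recorded. Node 15 to 5 mm is -66.7%. A 40 mm non-nodal lesion plus a 15 mm node, now 5 mm in total, is (55-5)/55 = -90.9%. With all other disease gone, both are irCR by the text and irPR by the table. Target nodes start at 15 mm or more and must end below 10 mm, so the fall always exceeds 1 - 10/15 = 33.3%. The patient stays a responder, and irRC ORR and DCR do not move, unless new measurable lesions have been added to the sum.

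**4. Size of the noise effect.** The documents give no measurement error, so a normal error on the sum with SD s is assumed, with no true change and the irPD row taken to prevail.

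For one later scan against one nadir scan, true sum m:
- Table: P(Z >= 0.2m / (s x sqrt(1 + 1.2^2))). With m = 10 and s = 1: 2/1.562 = 1.28, giving 10.0%. With m = 20: 4/1.562 = 2.56, giving 0.5%.
- Text, for sums in this range: about P(Z >= 5/(s x sqrt 2)) = P(Z >= 3.54), giving 0.02%.

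For a running nadir and four later scans, sums floored at 5 mm, s = 1 mm, 200,000 simulated patients:

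| True sum (mm) | Any irPD, table | Any irPD, text | Two successive, table | Two successive, text |
|---|---|---|---|---|
| 10 | 50% | 0.2% | 15% | <0.01% |
| 12 | 36% | 0.2% | 8% | <0.01% |
| 15 | 18% | 0.2% | 3% | <0.01% |
| 20 | 4% | 0.2% | 0.4% | <0.01% |

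The rates depend heavily on s. At 0.5 mm, any irPD by the table runs from 4% (10 mm) to 0% (20 mm). At 1.5 mm it is 50 to 74% for sums of 10 to 15 mm, against 7% by the text.

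**5. What reaches the analysis.** A single irPD followed by irSD or better is a pseudo-progression and is excluded (SAP 4.2.2.1). A single irPD does count if treatment then ends with no later assessment at 28 days or more (cPD2) or if the patient is still on treatment and it is unresolved at analysis (uPD). The main time-to-event analysis includes both (SAP 4.2.4.1). Confirmation therefore reduces the extra events without removing them.

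**The case against.** The strongest reply is that the full definitions stand directly above the table. Section 14.2.3 sends target evaluation to Section 14.2.4, and the pointer to Table 14-6 in the opening of 14.2.4 is attached to how non-target lesions contribute. A careful reader would apply the definitions and use the table only to combine components. This stands as a limit on the consequences: they arise only where the table is applied or programmed literally. It does not remove the conflict, because 14.2.3 names the table as the step that determines overall response, and the table's first column is a numeric threshold on the measured sum that disagrees with the text.

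A reader might infer three stronger things that the documents do not support:
- That a patient with nodal targets can never be irCR. Section 14.2.4 expressly allows it.
- That a rise of 20% or more but under 5 mm can only be irPD under the table. Where the sum is still at least 30% below baseline, the irPR row is also met.
- That the 18 to 50% figures are rates of analysed events. They count any irPD, before pseudo-progressions are removed, and cover only sums of 10 to 15 mm; at 20 mm the figure is 4%.

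It is also fair to say that the documents give neither a measurement SD nor the share of patients with a nadir sum below 25 mm, so no trial-level effect can be computed.

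**Conclusion.** The conflict is real on both points, and neither the protocol nor the SAP resolves it. The irPD difference is confined to nadir sums below 25 mm. The irCR difference shifts patients between irCR and irPR and leaves irRC ORR and DCR unchanged, except where new measurable lesions are in the sum. The affected outputs are secondary: irRC PFS, DOR and BOR. The Phase II primary endpoint, ORR by RECIST 1.1, uses Table 14-1, which carries both conditions, so it, its operating characteristics and the sample size are untouched.

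The thresholds and worked records follow from the documents alone. The simulated rates rest on an assumed independent normal error, a truly stable tumour and the irPD row prevailing. They show direction and order of size, not an expected count. The point should be corrected, but it does not put the trial's main conclusion at risk.

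**What to change.** 1. Reconcile Table 14-6 with Section 14.2.4 so that one rule applies to irPD, irSD and irCR, and state which row prevails when the irPD and irPR rows are both met.
2. State in SAP 4.2 which rule defines irPD and irCR for the irRC endpoints. The Section 14.2.4 definitions match RECIST Table 14-1 on both conditions, which bears on keeping the two sets of results comparable.
3. Check recorded irRC responses against the stored diameters, at least where the nadir sum is below 25 mm or a target is nodal. Report discrepancies as a sensitivity analysis of irRC PFS, DOR and BOR, leaving the investigators' records as they are. The SAP describes no such check for irRC, so it has to be added.
4. For the use of irPD in treatment discontinuation, the two passages must be reconciled; nothing further is proposed here.

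The cost is wording in one appendix table, a short SAP entry and a programmed check on diameters already collected. No new data are needed.
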